4.6.1. Clinical Variables

Clinical variables such as viral detection, viral shedding, and solicited symptoms and laboratory findings that are a part of the definition of symptomatic influenza virus infection, are assessed at each study day during the confinement period, after the day of study challenge. Symptoms are also assessed in the clinic visit on Day 15.

Virologic assessments are done at screening (Days -45 to -3), baseline (Days -2 and -1), and then repeated daily from Days 2-8 during the confinement period or for a longer period if still RT-PCR positive for influenza on Days 7 or 8 until two negative swabs are confirmed, at least 12 hours apart, consecutively. Only qualitative RT-PCR is performed at the screening visit, but subsequently nasopharyngeal (NP) swab samples are collected for quantitative RT-PCR as well. Quantitative RT-PCR (qRT-PCR) will be conducted by a research laboratory at Duke University. Qualitative RT-PCR is conducted via multiplex respiratory virus assay (BIOFIRE® FILMARRAY® respiratory panel by bioMérieux or Luminex xTAG®) on NP swabs at the local clinical site. Qualitative and quantitative RT-PCR for influenza from NLF specimens and quantitative viral culture from NP swabs and/or NLF specimens may be performed as well; these would be analyzed subsequently to compilation of the primary CSR, if the assays are performed.

Symptomatic influenza infection is assessed using a Modified Jackson score (MJS) collected by study staff twice a day (approximately 8 AM and after 3 PM) from Day -2 until the time of discharge, and again at the Day 15 visit to assess any ongoing symptoms. [Figure 4](#) displays the MJS investigator tool for assessing symptoms. Fever and lymphopenia, both included among the MJS symptoms for determining the symptomatic influenza attack rate, are assessed separately from the MJS form.

An additional validated, patient-reported outcome (PRO) measure to standardize assessment of influenza symptoms in clinical research (i.e., FLU-PRO Survey Instrument and Validation Diary) is to be completed by participants once a day (after 3:00 PM) from Day -2 through Day 15. The investigators review the FLU-PRO and Validation Diary at the Day 15 visit to assess any ongoing symptoms. The FLU-PRO questionnaire is presented in [Figure 5](#) for reference.

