5. GENERAL STATISTICAL CONSIDERATIONS

5.1. General Principles

The challenge period is defined as the day of study challenge (Day 1) through discharge from the confinement period (Day 8 or later).

Continuous variables will generally be summarized using the following descriptive statistics: non-missing sample size (denoted by “n”), mean or geometric mean, standard deviation, minimum, median, and maximum. Titers will be summarized with geometric means, first across replicates to compute one value for each individual sample and then across participants within clinical outcome groups. The frequencies and percentages (based on the non-missing sample size) of observed levels will be reported for categorical measures. Data listings will typically be sorted by site or other grouping variable (e.g. infection status), participant, and by visit number within participant, where appropriate. All tables will be annotated with the total population size relevant to that table, including any missing observations.

For continuous variables, confidence intervals will be computed based on the t-distribution, unless the data appear especially non-normal and the sample sizes for the analysis are insufficient to apply the central limit theorem. Bootstrap confidence intervals may be calculated instead if the t-distribution is determined to be unsuitable. For binary variables, confidence intervals will be computed using the exact Clopper-Pearson method.

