7.1.2. Influenza Symptoms

The maximum severity of influenza symptoms during the challenge period, reported as part of the Modified Jackson Score and used to determine the AR, will be summarized by challenge dose group in [Table 15](#), and separately by infection status (see [Section 3.2.3](#)) in [Table 16](#) and [Figure 7](#) (infected participants) and [Table 17](#) and [Figure 8](#) (uninfected participants). Symptoms reported on Study Day 15 will be presented similarly in [Table 18](#) and [Table 19](#). Symptoms over the challenge period will also be summarized by infection status, independent of challenge dose group, in [Table 20](#), and Day 15 symptoms will be presented in [Table 21](#).

New-onset symptoms (see [Section 3.2.3](#)) among infected participants will be summarized in [Figure 9](#), and the maximum severity of symptoms will be summarized by concurrent infection status in [Table 26](#). Wilcoxon signed rank tests will be used to compare maximum severities among infected participants: pre-infection to during infection, post-infection to during infection, and pre-infection to post-infection, in [Table 27](#). No p-value adjustment is planned for multiple comparisons, but the number of comparisons made will be considered when interpreting the results. Current/concurrent infection status is defined in [Section 3.2.3](#).

The maximum symptom severities reported for each study day during the challenge period and at any point post-challenge will be summarized for currently infected participants, separately by challenge dose group in [Table 22](#) through [Table 25](#). At baseline and Day 1, all participants will be included in these summaries, as a comparison for post-infection symptoms.

Total MJS scores during the challenge period will be presented by study day and challenge group in [Figure 10](#), with RT-PCR+ study days indicated with annotation in the given cell.

MJS symptoms will be presented in detail in [Listing 8](#).

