7. Participants will remain in the confinement unit for a minimum of seven days after the date of challenge. Participants will leave the unit after they meet the following discharge criteria: two consecutive negative NP swabs collected 12 hours apart (that are performed on Study Day 6 or thereafter) for influenza A by qualitative RT-PCR performed by the local clinical laboratory, are afebrile (< 100.6°F/38.1°C), have SpO₂ ≥ 95% on room air, show no moderate or severe influenza signs or symptoms by clinical evaluation, and are clinically and hemodynamically stable for 48 hours. Participants who do not meet discharge criteria on Study Day 8 will remain in the confinement unit until the criteria are met. Study procedures for the confinement unit will be the same as on Study Day 8, except for no NLF collection or additional blood draws unless clinically indicated.
8. A treatment course of oseltamivir phosphate or baloxavir marboxil will be provided to all participants who do not have two consecutive negative NP swabs by qualitative RT-PCR for influenza by Study Day 6. Treatment will begin as early as Study Day 6, or thereafter if indicated, or earlier if terminates study prior to Study Day 8.
9. Height and weight will be measured at Screening.
10. Concomitant medications taken within 90 days prior to signing the ICF are collected.
11. Clinical evaluation (including oral/pharyngeal, neck, lung and heart exam), and symptom evaluation daily while in the confinement unit. An otoscopic exam will be performed at baseline and as needed.
12. Oral temperature, blood pressure, pulse, and respiratory rate will be assessed approximately every 8 hours while in the confinement unit (from 12:00AM – 11:59PM), while the participants are awake, and as clinically indicated.
13. Peripheral oxygen saturation (SpO₂) on room air at screening, on admission, and when oral temperature, blood pressure, pulse, and respiratory rate are assessed through the confinement period and at follow-up visits.
14. Self-assessment using FLU-PRO and Validation Diary to be performed after 3:00 pm on the Day -2 and after 3:00 pm each day of confinement and through Day
15. Modified Jackson Score to be obtained on the evening of Day -2 and in the morning and afternoon of each day of confinement (Approximately at 8:00 AM and after 3:00 PM) and on Day 15 during visit. Assure AM assessment on Study Day 1 is performed pre-challenge.

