	None	x (x.x)	-	x (x.x)	-	x (x.x)	-	x (x.x)	-
	1: Just Noticeable	x (x.x)	-	x (x.x)	-	x (x.x)	-	x (x.x)	-
	2: Bothersome from Time to Time	x (x.x)	-	x (x.x)	-	x (x.x)	-	x (x.x)	-
	3: Bothersome Most or All of the Time	x (x.x)	-	x (x.x)	-	x (x.x)	-	x (x.x)	-
Lymphopenia ^c	Any Severity	x (x.x)	(x.x, x.x)	x (x.x)	(x.x, x.x)	x (x.x)	(x.x, x.x)	x (x.x)	(x.x, x.x)

Symptom	Maximum Severity	10 ⁴ TCID ₅₀ Challenge Virus (N=X)		10 ⁵ TCID ₅₀ Challenge Virus (N=X)		10 ⁶ TCID ₅₀ Challenge Virus (N=X)		Sham Inoculum (N=X)	
		n (%)	95% CI	n (%)	95% CI	n (%)	95% CI	n (%)	95% CI
	None	x (x.x)	-	x (x.x)	-	x (x.x)	-	x (x.x)	-
	Mild	x (x.x)	-	x (x.x)	-	x (x.x)	-	x (x.x)	-
	Moderate	x (x.x)	-	x (x.x)	-	x (x.x)	-	x (x.x)	-
	Severe	x (x.x)	-	x (x.x)	-	x (x.x)	-	x (x.x)	-

Notes: N = Number of participants in the Safety population; n = Number of participants reporting each symptom.

^aAs reported on the Modified Jackson Score (MJS) tool; maximum severity across the challenge period reported.

^bAs part of vital signs assessments, with temperature collected three times daily during the challenge period. Fever and feverishness (from MJS) contribute as one item towards the Modified Jackson Score.

^cAs part of clinical safety laboratory assessments, on Study Days 2, 4, 8, and any supplemental visits during the challenge period.

Table 16: Maximum Severity of Influenza Symptoms Reported During the Challenge Period by Challenge Dose Group, Infected Participants in the Safety Population

Symptom	Maximum Severity	10 ⁴ TCID ₅₀ Challenge Virus, RT-PCR+ (N=X)		10 ⁵ TCID ₅₀ Challenge Virus, RT-PCR+ (N=X)		10 ⁶ TCID ₅₀ Challenge Virus, RT-PCR+ (N=X)		Any Active Challenge Virus Dose, RT-PCR+ (N=X)		Sham Inoculum, RT-PCR+ (N=X)	
		n (%)	95% CI	n (%)	95% CI	n (%)	95% CI	n (%)	95% CI	n (%)	95% CI
Any Symptom	Any Severity	x (x.x)	(x.x, x.x)	x (x.x)	(x.x, x.x)	x (x.x)	(x.x, x.x)	x (x.x)	(x.x, x.x)	x (x.x)	(x.x, x.x)
	None	x (x.x)	-	x (x.x)	-	x (x.x)	-	x (x.x)	-	x (x.x)	-
	Mild or Just Noticeable	x (x.x)	-	x (x.x)	-	x (x.x)	-	x (x.x)	-	x (x.x)	-
	Moderate or Bothersome from Time to Time	x (x.x)	-	x (x.x)	-	x (x.x)	-	x (x.x)	-	x (x.x)	-
	Severe or Bothersome Most or All of the Time	x (x.x)	-	x (x.x)	-	x (x.x)	-	x (x.x)	-	x (x.x)	-
Runny Nose ^a	Any Severity	x (x.x)	(x.x, x.x)	x (x.x)	(x.x, x.x)	x (x.x)	(x.x, x.x)	x (x.x)	(x.x, x.x)	x (x.x)	(x.x, x.x)
	None	x (x.x)	-	x (x.x)	-	x (x.x)	-	x (x.x)	-	x (x.x)	-
	1: Just Noticeable	x (x.x)	-	x (x.x)	-	x (x.x)	-	x (x.x)	-	x (x.x)	-

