	1: Just Noticeable	x (x.x)	-	x (x.x)	-

Symptom	Severity	RT-PCR+ at Least Twice (N=X)		RT-PCR+ Less than Twice (N=X)	
		n (%)	95% CI	n (%)	95% CI
	2: Bothersome from Time to Time	x (x.x)	-	x (x.x)	-
	3: Bothersome Most or All of the Time	x (x.x)	-	x (x.x)	-
Malaise (tiredness) ^a	Any Severity	x (x.x)	(x.x, x.x)	x (x.x)	(x.x, x.x)
	0: None	x (x.x)	-	x (x.x)	-
	1: Just Noticeable	x (x.x)	-	x (x.x)	-
	2: Bothersome from Time to Time	x (x.x)	-	x (x.x)	-
	3: Bothersome Most or All of the Time	x (x.x)	-	x (x.x)	-
Body Ache ^a	Any Severity	x (x.x)	(x.x, x.x)	x (x.x)	(x.x, x.x)
	0: None	x (x.x)	-	x (x.x)	-
	1: Just Noticeable	x (x.x)	-	x (x.x)	-
	2: Bothersome from Time to Time	x (x.x)	-	x (x.x)	-
	3: Bothersome Most or All of the Time	x (x.x)	-	x (x.x)	-
Chills ^a	Any Severity	x (x.x)	(x.x, x.x)	x (x.x)	(x.x, x.x)
	0: None	x (x.x)	-	x (x.x)	-
	1: Just Noticeable	x (x.x)	-	x (x.x)	-
	2: Bothersome from Time to Time	x (x.x)	-	x (x.x)	-
	3: Bothersome Most or All of the Time	x (x.x)	-	x (x.x)	-
Feverish ^a	Any Severity	x (x.x)	(x.x, x.x)	x (x.x)	(x.x, x.x)
	0: None	x (x.x)	-	x (x.x)	-
	1: Just Noticeable	x (x.x)	-	x (x.x)	-
	2: Bothersome from Time to Time	x (x.x)	-	x (x.x)	-
	3: Bothersome Most or All of the Time	x (x.x)	-	x (x.x)	-
Fever ^b	Any Severity	x (x.x)	(x.x, x.x)	x (x.x)	(x.x, x.x)
	None	x (x.x)	-	x (x.x)	-
	Mild	x (x.x)	-	x (x.x)	-
	Moderate	x (x.x)	-	x (x.x)	-
	Severe	x (x.x)	-	x (x.x)	-
Shortness of Breath ^a	Any Severity	x (x.x)	(x.x, x.x)	x (x.x)	(x.x, x.x)
	0: None	x (x.x)	-	x (x.x)	-
	1: Just Noticeable	x (x.x)	-	x (x.x)	-
	2: Bothersome from Time to Time	x (x.x)	-	x (x.x)	-
	3: Bothersome Most or All of the Time	x (x.x)	-	x (x.x)	-
Earache ^a	Any Severity	x (x.x)	(x.x, x.x)	x (x.x)	(x.x, x.x)
	0: None	x (x.x)	-	x (x.x)	-
	1: Just Noticeable	x (x.x)	-	x (x.x)	-

Symptom	Severity	RT-PCR+ at Least Twice (N=X)		RT-PCR+ Less than Twice (N=X)	
		n (%)	95% CI	n (%)	95% CI
	2: Bothersome from Time to Time	x (x.x)	-	x (x.x)	-
	3: Bothersome Most or All of the Time	x (x.x)	-	x (x.x)	-
Lymphopenia ^c	Any Severity	x (x.x)	(x.x, x.x)	x (x.x)	(x.x, x.x)
	None	x (x.x)	-	x (x.x)	-
	Mild	-	-	-	-
	Moderate	-	-	-	-
	Severe	-	-	-	-

Notes: N = Number of participants in the Safety population with the given infection status; n = Number of participants reporting each symptom, regardless of timing with respect to RT-PCR positivity.

^aAs reported on the Modified Jackson Score (MJS) tool; maximum severity across the challenge period reported.

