Notes: N = Number of participants in the Safety population RT-PCR+ on the given study day; n = Number of participants reporting each symptom. **Prior to Day 2, all participants included as symptom background.**

^a As reported on the Modified Jackson Score (MJS) tool.

^b As part of vital signs assessments, with temperature collected three times daily during the challenge period. Fever and feverishness (from MJS) contribute as one item towards the Modified Jackson Score.

^c As part of clinical safety laboratory assessments, on Study Days 2, 4, 8, and any supplemental visits during the challenge period.

Similar Tables:

Table 23: Maximum Severity of Participant-Reported Influenza Symptoms by Study Day, 10⁵ TCID₅₀ Challenge Virus Group, Currently Infected Participants in the Safety Population

Table 24: Maximum Severity of Participant-Reported Influenza Symptoms by Study Day, 10⁶ TCID₅₀ Challenge Virus Group, Currently Infected Participants in the Safety Population

Table 25: Maximum Severity of Participant-Reported Influenza Symptoms by Study Day, Sham Inoculum Group, Currently Infected Participants in the Safety Population

Table 26: Maximum Severity of Influenza Symptoms Reported During the Challenge Period by Current Infection Status, Safety Population

Symptom	Severity	Pre-Infection (N=X)		Current Infection (N=X)		Post-Infection (N=X)		Uninfected (N=X)	
		n (%)	95% CI	n (%)	95% CI	n (%)	95% CI	n (%)	95% CI
Any Symptom	Any Severity	x (x.x)	(x.x, x.x)	x (x.x)	(x.x, x.x)	x (x.x)	(x.x, x.x)	x (x.x)	(x.x, x.x)
	None	x (x.x)	-	x (x.x)	-	x (x.x)	-	x (x.x)	-
	Mild or Just Noticeable	x (x.x)	-	x (x.x)	-	x (x.x)	-	x (x.x)	-
	Moderate or Bothersome from Time to Time	x (x.x)	-	x (x.x)	-	x (x.x)	-	x (x.x)	-
	Severe or Bothersome Most or All of the Time	x (x.x)	-	x (x.x)	-	x (x.x)	-	x (x.x)	-
Runny Nose ^a	Any Severity	x (x.x)	(x.x, x.x)	x (x.x)	(x.x, x.x)	x (x.x)	(x.x, x.x)	x (x.x)	(x.x, x.x)
	0: None	x (x.x)	-	x (x.x)	-	x (x.x)	-	x (x.x)	-
	1: Just Noticeable	x (x.x)	-	x (x.x)	-	x (x.x)	-	x (x.x)	-
	2: Bothersome from Time to Time	x (x.x)	-	x (x.x)	-	x (x.x)	-	x (x.x)	-
	3: Bothersome Most or All of the Time	x (x.x)	-	x (x.x)	-	x (x.x)	-	x (x.x)	-
Stuffy Nose ^a	Any Severity	x (x.x)	(x.x, x.x)	x (x.x)	(x.x, x.x)	x (x.x)	(x.x, x.x)	x (x.x)	(x.x, x.x)
	0: None	x (x.x)	-	x (x.x)	-	x (x.x)	-	x (x.x)	-
	1: Just Noticeable	x (x.x)	-	x (x.x)	-	x (x.x)	-	x (x.x)	-
	2: Bothersome from Time to Time	x (x.x)	-	x (x.x)	-	x (x.x)	-	x (x.x)	-

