	2: Bothersome from Time to Time	x (x.x)	-	x (x.x)	-
	3: Bothersome Most or All of the Time	x (x.x)	-	x (x.x)	-
Feverish ^a	Any Severity	x (x.x)	(x.x, x.x)	x (x.x)	(x.x, x.x)
	0: None	x (x.x)	-	x (x.x)	-
	1: Just Noticeable	x (x.x)	-	x (x.x)	-
	2: Bothersome from Time to Time	x (x.x)	-	x (x.x)	-

Symptom	Severity	Duke University (N=X)		University of Maryland (N=X)	
		n (%)	95% CI	n (%)	95% CI
Fever ^b	3: Bothersome Most or All of the Time	x (x.x)	-	x (x.x)	-
	Any Severity	x (x.x)	(x.x, x.x)	x (x.x)	(x.x, x.x)
	None	x (x.x)	-	x (x.x)	-
	Mild	x (x.x)	-	x (x.x)	-
	Moderate	x (x.x)	-	x (x.x)	-
Shortness of Breath ^a	Severe	x (x.x)	-	x (x.x)	-
	Any Severity	x (x.x)	(x.x, x.x)	x (x.x)	(x.x, x.x)
	0: None	x (x.x)	-	x (x.x)	-
	1: Just Noticeable	x (x.x)	-	x (x.x)	-
	2: Bothersome from Time to Time	x (x.x)	-	x (x.x)	-
Earache ^a	3: Bothersome Most or All of the Time	x (x.x)	-	x (x.x)	-
	Any Severity	x (x.x)	(x.x, x.x)	x (x.x)	(x.x, x.x)
	0: None	x (x.x)	-	x (x.x)	-
	1: Just Noticeable	x (x.x)	-	x (x.x)	-
	2: Bothersome from Time to Time	x (x.x)	-	x (x.x)	-
Lymphopenia ^c	3: Bothersome Most or All of the Time	x (x.x)	-	x (x.x)	-
	Any Severity	x (x.x)	(x.x, x.x)	x (x.x)	(x.x, x.x)
	None	x (x.x)	-	x (x.x)	-
	Mild	x (x.x)	-	x (x.x)	-
	Moderate	x (x.x)	-	x (x.x)	-
	Severe	x (x.x)	-	x (x.x)	-

Notes: N = Number of participants in the Safety population with RT-PCR+ results on at least two study days; n = Number of participants reporting each symptom, regardless of timing with respect to RT-PCR positivity.

^a As reported on the Modified Jackson Score (MJS) tool; maximum severity across the challenge period reported.

^b As part of vital signs assessments, with temperature collected three times daily during the challenge period. Fever and feverishness (from MJS) contribute as one item towards the Modified Jackson Score.

^c As part of clinical safety laboratory assessments, on Study Days 2, 4, 8, and any supplemental visits during the challenge period.

Similar Table:

Table 45: Maximum Severity of Influenza Symptoms Reported During the Challenge Period by Clinical Site, Uninfected Participants in the Safety Population

Table 46: Symptoms Predicting Infection Status Lasso Logistic Regression Model to Predict Infection Status, Safety Population

Model Parameter	Parameter Estimate	SE	p-value	Odds Ratio	95% CI
Intercept	x.xx	x.xx	x.xxx	-	-
[Symptom x]	x.xx	x.xx	x.xxx	x.xx	(x.xx, x.xx)
[Symptom y]	x.xx	x.xx	x.xxx	x.xx	(x.xx, x.xx)

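### The SAP's challenge period includes the Day 1 assessments made before inoculation, so pre-challenge scores can enter supporting symptom tables and, for uninfected participants only, the exploratory lasso model

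*SAP*

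**What the plan says.** **Period.** SAP 5.1 (General Principles) gives the only explicit definition: "The challenge period is defined as the day of study challenge (Day 1) through discharge from the confinement period (Day 8 or later". It makes no exception for assessments before inoculation.

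**Timing of assessments.** SAP 4.6.1 says the MJS is "collected by study staff twice a day (approximately 8 AM and after 3 PM) from Day -2 until the time of discharge". Footnote 15 of the Schedule of Activities (SAP Table 1, and the same footnote in the protocol) adds: "Assure AM assessment on Study Day 1 is performed pre-challenge". SAP 4.6.2 lists vital signs on Day 1 before challenge as well as after it. The FLU-PRO is completed once daily after 3 PM and asks about the preceding 24 hours.

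**Summary measure.** SAP 7.1.2, under Primary Clinical Analysis, reports "The maximum severity of influenza symptoms during the challenge period, reported as part of the Modified Jackson Score and used to determine the AR". Table 15, footnote a, repeats the rule: "As reported on the Modified Jackson Score (MJS) tool; maximum severity across the challenge period reported". The note to Table 20 reads: "n = Number of participants reporting each symptom, regardless of timing with respect to RT-PCR positivity".

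**Other treatments of Day 1.**
- Tables 22-25 have a Baseline column and a separate column headed Day 1 (Post-Challenge), with the note "Prior to Day 2, all participants included as symptom background".
- Table 28 labels Day 1 as baseline, and its footnote gives the challenge period as Days 2 to 8+.
- Table 59 labels Days 1-8 as the challenge period.
- The attack-rate score in Table 14 uses Days 2-6, 3-7 or 4-8 only.

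**The concern.** A maximum over a period can only stay the same or rise when an assessment is added. If the period opens before inoculation, a complaint present at about 8 AM on Day 1 and gone by the afternoon is tabulated as a challenge-period symptom. A worse morning score also fixes the reported severity category.

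Three things are at stake.

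1. **Separation of baseline from outcome.** Primary objective 3 is to document symptoms at baseline and after challenge. Tables 15-17 have no baseline column, so a reader could not see that part of one had been folded into the other.
2. **Background in uninfected participants.** Tables 17 and 45 describe this group. The new-onset rule in SAP 3.2.3 compares with baseline for infected participants only, so nothing corrects the uninfected tables.
3. **An uneven effect in the lasso model (SAP 7.2.3).** Uninfected participants contribute their maximum over the whole challenge period, and infected participants only over current infection. The pre-inoculation form can therefore enter one outcome class and not the other, and the cutpoint is meant for a later validation.

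Because the SAP also labels Day 1 in conflicting ways, two programmers could produce different versions of these tables.

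**Working it through.** The plan states no figure on this point, so there is none to reproduce. The check has three steps.

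**Step 1: forms inside the defined period.** With two MJS forms a day, Days 1-8 hold 8 × 2 = 16 scheduled forms. By footnote 15, one of them (Day 1 AM) precedes inoculation. Restricting to forms after inoculation leaves 15; starting on Day 2 would leave 14.

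**Step 2: outputs that inherit the form.**

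| Output | Can a pre-inoculation Day 1 assessment enter? |
|---|---|
| Tables 15-17, 20, 44-45; Figures 7-8 | Yes: maximum over the challenge period |
| Tables 41-42 | Yes: MJS as above; the Day 1 FLU-PRO recall spans inoculation |
| Table 26, Uninfected column | Yes |
| Lasso predictors | Yes, uninfected participants only |
| Table 14 attack rate and maximum cumulative MJS | No: windows start on Day 2 or later |
| Tables 18, 19, 21 (Day 15) | No |
| Figure 9 (new onset, infected) | No: starts at first RT-PCR positivity |
| Tables 22-25 | Day 1 is shown in its own column |
| Lymphopenia rows | No: scheduled laboratory days are 2, 4 and 8 |

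**Step 3: possible size.** The documents give no background symptom rate, so this step rests on assumptions. Let q be the chance that a symptom is on the Day 1 AM form and L the chance that it is on at least one later form, taken as independent. The any-severity percentage is then 1 − (1 − q)(1 − L) with the morning form and L without it. The excess is q(1 − L).

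Assume a constant daily background p, split evenly over the two forms of a day. Then q = 1 − (1 − p)^0.5. Seven and a half days remain, so L = 1 − (1 − p)^7.5, and with the form included the percentage is 1 − (1 − p)^8.

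| p per day | With Day 1 AM | Without | Difference (points) | Of 12 | Of 36 |
|---|---|---|---|---|---|
| 5% | 33.7% | 31.9% | 1.7 | 0.2 | 0.6 |
| 10% | 57.0% | 54.6% | 2.3 | 0.3 | 0.8 |
| 15% | 72.8% | 70.4% | 2.3 | 0.3 | 0.8 |
| 20% | 83.2% | 81.2% | 2.0 | 0.2 | 0.7 |

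The last two columns multiply the difference by 12 and 36, the smallest and largest targeted active group sizes at the two lower doses. Each entry is below one participant.

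If q and L are allowed to vary freely, with q from 5% to 30% and L from 20% to 80%, the excess runs from 0.05 × 0.20 = 1 point to 0.30 × 0.80 = 24 points. The top of that range needs a symptom to be more likely on the single morning form (30%) than on all later forms together (20%), which is hard to believe of a steady background. Persistence works the other way: someone symptomatic on the Day 1 AM form will often report the symptom again, and the form then adds nothing to the any-severity count.

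**The case against.** The case against is that this is loose wording rather than a decision to count pre-inoculation scores, and that the tables involved carry little weight.

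- SAP 4.6.1 places the clinical variables on confinement days after the day of challenge. SAP 4.6.2 has solicited symptoms collected from challenge onward. Table 28 glosses the period as Days 2 to 8+, and the footnotes to Tables 43 and 49 as Days 2 to 8.
- The endpoints listed for primary objective 3 are the computed total MJS and the percentage classed as symptomatic. Both are reported in Table 14 over windows that exclude Day 1. None of the affected tables is flagged for the topline report.
- For fever the practical risk is small. Entry requires an oral temperature below 100.6°F, Grade 1 fever starts at 100.6°F, and eligibility is reviewed again on Day 1.

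Most of this stands and limits the importance of the point. It does not remove it. None of the cited text excludes the Day 1 AM form from the maxima, and SAP 4.6.1 itself has MJS collection running from Day -2. The conflicting glosses are a reason to state the rule.

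A reader might infer more than the documents support:

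- **That the attack rate or escalation is inflated.** Every scoring window starts on Day 2 or later.
- **That background complaints are attributed to the virus.** The table titles refer to reporting during the challenge period, not to causation, and Table 15 prints a sham column beside the doses.
- **That Table 22 treats the same pre-inoculation scores as background.** Its Day 1 column is headed as post-challenge and stands apart from Baseline. The conflict is one of labels.
- **That the effect is 3.5 to 4.8 points.** That comes from comparing eight whole days with seven on the same assumptions, but the Day 1 afternoon form follows inoculation.

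**Conclusion.** The point holds as a definitional fault with limited consequences. Under the SAP's only explicit definition, a pre-inoculation MJS or temperature can set a challenge-period maximum, and the SAP's own labels for Day 1 disagree. The effect falls on supporting descriptive tables and figures in every group, sham included, and on the exploratory lasso model. In the lasso it is one-sided: it can only raise the predictors of uninfected participants.

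The size cannot be known from the documents. With an independent, constant background of 5-20% per day, it is about 2 percentage points on any severity, or less than one participant in a group of 12 to 36. Persistence of symptoms would probably make it smaller. No dose decision or primary attack-rate estimate depends on it. It is still worth correcting, because the correction is nearly free and the tables would otherwise depend on a programmer's reading.

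**What to change.** Add one rule to SAP 5.1, along these lines: *for symptom, fever and lasso-predictor maxima, the challenge period comprises assessments made after inoculation on Day 1 through discharge; the Day 1 morning MJS and the Day 1 vital signs taken before challenge are baseline; the Day 1 FLU-PRO is background, because its recall spans inoculation.*

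Apply it to Tables 15-17, 20, 41-42 and 44-45, Figures 7-8, the Uninfected column of Table 26 and the lasso predictors in SAP 7.2.3. Then align the Day 1 labels in Tables 22-25 and Table 28 with the rule.

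A Day 2 to Day 8 window would also remove the contamination, but it would discard the Day 1 afternoon MJS and anything recorded after Day 8 in participants who stay longer. It is not needed.

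**Cost.** One derivation rule, some label edits and slightly lower symptom percentages; no new data. Setting the Day 1 FLU-PRO aside loses little, since the Day 2 entry looks back 24 hours to about the afternoon of Day 1.
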